# 9.3. **Populations for Analyses**

The following populations are defined:

Population	Description	
mITT	All randomized participants who have nonmissing baseline ATHS. This population will be used as the full analysis set.	
РР	All participants in the mITT population with nonmissing primary effectiveness endpoint (ie, nonmissing ATHS for Month 6 for each temple) and with no significant protocol deviations that could affect the primary effectiveness endpoint. A significant deviation that occurs after the primary endpoint would not lead to exclusion from the PP analysis.	
Safety	All randomized participants who have at least 1 study treatment intervention (ie, VOLUMA with Lidocaine or no treatment).	

Analyses of safety variables will be performed on the safety population, with participants grouped as treated. Unless specified otherwise, all other analyses will be performed on the mITT population, with participants grouped as randomized. The PP population will be used to perform PP sensitivity analysis, with participants grouped as randomized, for the primary endpoint.

## 9.4. Statistical Analyses

The SAP will be finalized before database lock and will include a more technical and detailed description of the statistical analyses described in this section. This section is a summary of the planned statistical analyses of the most important endpoints, including primary and secondary endpoints.

#### 9.4.1. General Considerations

The effectiveness analyses will be based on the mITT population in general, and PP sensitivity analysis of the primary endpoint will be based on the PP population. Baseline for effectiveness is defined as the last nonmissing effectiveness assessment before randomization.

All statistical tests will be 2-sided hypothesis tests performed at the 5% level of significance for main effects. A gatekeeping procedure will be used for hypothesis testing of the primary endpoint (ATHS responder) and 2 of the secondary endpoints (responder rates for EI and participant assessments of GAIS) following a predefined sequence to control the overall type I error rate at the 0.05 level. The primary hypothesis must be rejected in order to test the responder rate for EI assessment of GAIS. Additionally, statistical significance must be established for the responder rate for EI assessment of GAIS in order to assess the hypothesis for the responder rate for participant assessment of GAIS.

#### 9.4.2. Primary Endpoint

#### 9.4.2.1. Definition of Endpoint

Primary effectiveness endpoint:

• Responder status based on the EI's live assessment of temple hollowing using ATHS at Month 6 after last treatment for treatment group and after randomization for control group, where a "responder" is a participant with at least 1-grade improvement on the ATHS in both temples.

#### 9.4.2.2. Main Analytical Approach

The primary effectiveness analysis will be performed on the mITT population. The study intervention will be determined to be clinically effective if the following criterion is met:

• The ATHS responder rate for the treatment group is statistically superior to the responder rate for the control group at Month 6

Two-sided Fisher's exact test with 5% significance level will be used to compare responder rates between treatment and the control group. If the 2-sided p-value is  $\leq 0.05$ , which implies that the responder rate is different for treatment than for the control group, and the point estimate of the responder rate for the treatment group is greater than for the control group, then treatment will be considered clinically effective. In addition, responder rates and 95% CIs will be displayed within and between treatment and control groups.

If there are any mITT participants with missing primary effectiveness endpoint, the following missing-data handling method is planned for the primary analysis.

- Multiple imputation by the fully conditional specification method for ordinal data (via SAS procedure MI with FCS logistic statement) will be done with 5 imputed datasets for participants with missing primary endpoint, using the model below:
- Month 6 ATHS =  $\beta_0 + \beta_1 \times \text{Baseline ATHS} + \beta_2 \times \text{Month 1 ATHS} + \beta_3 \times \text{Month 3 ATHS}$
- Intermittent missing ATHS at Month 1 and Month 3 will be imputed by similar models using ATHS at previous visits as covariates.
- The imputation will be performed by treatment group and by side (left and right).
- After imputation, the changes from baseline will be calculated, from which the responder status will be determined.
- Analyses of individual imputed datasets will be performed by SAS procedure FREQ and then pooled by SAS procedure MIANALYZE to display combined responder rates and 95% CIs within and between treatment and control groups and to generate an associated p-value for the comparison of responder rates between groups.

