# 9.2. Sample Size Determination

The primary effectiveness measure is the change from baseline on the 5-point ATHS at Month 6. The change can range from -4 to +2. The primary effectiveness variable is the ATHS responder status, which is determined by an improvement of 1 grade or more (ie, a change score of -4 to -1) in both temples.

Under a 2:1 randomization ratio, a total of 90 participants in the treatment group and 45 participants in the control group at the primary timepoint will provide at least 90% power to detect a difference of 30% in the responder rates between the groups. This calculation is based on a 2-sided Fisher's exact test at the 5% level, using responder rates of 65% and 35% for both temples simultaneously for participants in the treatment and control groups, respectively. The assumption of a 65% treatment responder rate is a conservative estimate based on the observed responder rate in previous filler studies for other facial areas. Also, while a 30% difference from control is greater than a minimally important difference, a 35% responder rate is a reasonable upper limit of expectation for the control group, based on validation results of the ATHS and control group responder rates observed in previous filler studies. Furthermore, assuming a dropout rate of 20% after randomization through the Month 6 visit, 168 randomized participants are needed, with 112 participants in the treatment group and 56 participants in the control group (2:1 ratio).

If the underlying true responder rate is 65%, 90 participants in the treatment group results in a binomial likelihood of 86.5% to observe a responder rate of at least 60%.

With up to 9 investigational sites planned, it is recommended that no site randomize more than twice the proportional share of 1 more site =  $2 \times [168/(n+1)]$ . The recommended minimum is 8 participants per site, which will guarantee that each treatment group has at least 2 participants at each site (allowing for mixed randomization blocks of 3 and 6 that incorporate the 2:1 randomization ratio).

The commercial software PASS (2008, Version 8.0.13) was used for the power calculation. The sample size calculation used an inequality test for 2 proportions to demonstrate that the treatment group is superior to the control group.

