#### 9.4.3. Secondary Endpoints

Secondary effectiveness endpoints:

- Responder status based on the EI's assessment of the temple area using GAIS at Month 6 after last treatment for treatment group and after randomization for control group, where a "responder" is a participant with grade "improved" or "much improved" on GAIS.
- Responder status based on the participant's assessment of the temple area using GAIS at Month 6 after last treatment for treatment group and after randomization for control group, where a "responder" is a participant with grade "improved" or "much improved" on GAIS.
- Change from baseline on FACE-Q Satisfaction with Facial Appearance questionnaire at Month 6 after last treatment for treatment group and after randomization for control group.
- Change from baseline on FACE-Q Satisfaction with Temples questionnaire at Month 6 after last treatment for treatment group and after randomization for control group.

The following analysis will be performed for the secondary effectiveness endpoints:

- For the responder status based on the EI's and participant's assessments of GAIS at Month 6, the responder rates with 95% exact CI will be summarized, and p-value for between treatment group comparisons will be based on 2-sided Fisher's exact test using observed data.
- Change from baseline on participant responses on FACE-Q Satisfaction with Facial Appearance and with Temples questionnaires, for the Rasch-transformed score (0-100), will be analyzed using a repeated measures mixed-effects model, and the p-value for the between treatment group comparison will be provided for Month 6.

CONFIDENTIAL JUVÉDERM® VOLUMA® with Lidocaine injectable gel

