#### 8.3.2 Handling of Missing Data for the Primary Effectiveness Endpoint(s)

If there are any mITT participants with missing scores for the primary effectiveness endpoint, the following missing-data handling method is planned.

Step 1: The missing data will be imputed by treatment group and by side of the temple using the FCS method for ordinal data (via SAS procedure MI with FCS logistic statement). Thirty (30) imputed datasets will be generated, using *seed* = 1878701 and *nimpute* = 30 based on the following model:

Month 6 ATHS =  $\beta_0 + \beta_1 \times \text{Baseline ATHS} + \beta_2 \times \text{Month 1 ATHS} + \beta_3 \times \text{Month 3 ATHS}$ 

Step 2: With the FCS logistic statement in the MI procedure, each imputed dataset will have ATHS scores of 0, 1, 2, 3, or 4. After imputation, the changes from baseline will be calculated, from which the responder status in ATHS at Month 6 of CP will be determined. Intermittent missing ATHS at Month 1 and Month 3 will be imputed by similar models using ATHS at previous visits as covariates.

Step 3: Each complete (imputed) dataset obtained from Steps 1 and 2 will be analyzed using SAS procedure FREQ.

Step 4: The pooled results will be obtained using PROC MIANALYZE.

The aggregated responder rates by treatment group and the associated p-value and 95% CI will be presented to assess the difference in the ATHS responder rate at Month 6 of CP between VOLUMA and the no-treatment control. If the 2-sided p-value is  $\leq 0.05$ , then the ATHS responder rate at Month 6 in VOLUMA XC is statistically significantly different from that in the no-treatment control group.

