#### Table 6.Global Aesthetic Improvement Scale

The other secondary effectiveness measures are the participant responses on the FACE-Q questionnaires: Satisfaction with Facial Appearance and Satisfaction with Temples.

Change from baseline on participant responses on FACE-Q Satisfaction with Facial Appearance and with Temples questionnaires, for the Rasch-transformed score (0-100) will be analyzed using a mixed-effects model for repeated measures, and the nominal p-value for the between treatment group comparison will be provided for Month 6.

For FACE-Q Satisfaction with Facial Appearance questionnaire and FACE-Q Satisfaction with Temples questionnaire, the responses to all the items will be summed and converted to a Rasch-transformed score that ranges from 0 to 100 (higher score indicates increased satisfaction) using the algorithm developed by the FACE-Q scale developers.

For items with missing data (which includes selection of more than 1 response for an item, a response of non-applicable (N/A) or skipping a question), insert the unrounded mean of the completed items into the total sum score. The summed score including the imputation of missing items is rounded to the nearest integer and converted to the Rasch transformed score using the conversion table below. Higher scores reflect a better outcome. The converted score ranges from 0 (worst) to 100 (best). If less than 50% of the questions have been answered, then the overall score will be missing.

The secondary effectiveness endpoints will be analyzed based on mITT population based on the observed data.

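### The primary ATHS responder comparison is unadjusted for baseline ATHS grade: a modest, assumption-dependent loss of precision, not a validity error

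*Protocol*

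**What the plan says.** Primary endpoint. Protocol 9.4.2.2: "Two-sided Fisher's exact test with 5% significance level will be used to compare responder rates between treatment and the control group". If any Month 6 ATHS score is missing, scores are multiply imputed by arm and by temple, and SAP 8.3.2 Step 3 then says "Each complete (imputed) dataset obtained from Steps 1 and 2 will be analyzed using SAS procedure FREQ", with pooling by MIANALYZE. No covariate or stratum is named. The sensitivity analyses in SAP 8.3.4 are unadjusted Fisher tests, and neither document plans an effectiveness subgroup analysis.

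Baseline ATHS enters in two places only: the responder definition (change from baseline in both temples) and the imputation model for Month 6 ATHS. The mITT population (protocol 9.3, SAP Table 1) requires it to be present. Randomization is within site (protocol 6.3), and protocol Appendix 6 lists no stratification factor.

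Secondary endpoints. For both GAIS responder endpoints, protocol 9.4.3 says "p-value for between treatment group comparisons will be based on 2-sided Fisher's exact test using observed data". FACE-Q change from baseline "will be analyzed using a mixed-effects model for repeated measures" (SAP 8.4). Neither document lists any term of that model. The SAP calls its p-value nominal, and FACE-Q is outside the testing hierarchy.

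**The concern.** Response means a fall of at least one grade from an entry grade of 2, 3 or 4. A Grade 4 temple cannot be rated worse and a Grade 2 temple can, so rating error alone can produce apparent improvement at different rates by starting grade. Protocol 4.2.4 gives rater agreement only as above 0.60, and protocol 9.2 allows up to 35% response without treatment. Exclusion 1.01 also treats the achievable improvement as depending on the baseline score and the volume cap.

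If response does depend on starting grade, the unadjusted difference carries any chance imbalance in grade between arms and has a larger variance than it needs. Adjustment would need no new data. At stake is precision in the primary result, and some power.

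**Working it through.** **1. The plan's own figure.** Inputs from protocol 9.2: 90 evaluable treated and 45 evaluable controls; response of 65% and 35%; two-sided Fisher test at 5%. The claim is that this design "will provide at least 90% power to detect a difference of 30% in the responder rates between the groups". Exact enumeration over the two binomials gives 90.8% power, so the stated figure reproduces. The next smaller 2:1 design, 88/44, gives 89.8%.

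**2. Unadjusted precision.** p(1-p) = 0.65 × 0.35 = 0.2275 in both arms. Variance of the difference = 0.2275/90 + 0.2275/45 = 0.00758; SE = 0.0871; 95% CI half-width = 1.96 × 0.0871 = 17.1 points.

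**3. What stratifying could remove.** The documents give neither the grade mix nor the link between grade and response. Assume three equal strata, with response rates d below, at, and d above the overall rate in both arms. The share of outcome variance between strata is (2/3)d²/0.2275:
- d = 0.065: 0.0028/0.2275 = 1.2%
- d = 0.15: 0.0150/0.2275 = 6.6%
- d = 0.25: 0.0417/0.2275 = 18.3%

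Stratifying has its own cost of about 1-2% of variance, so the first case roughly breaks even. Simulated net reductions were about 6% at ±15 points and 17% at ±25.

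**4. Simulated power, 90/45, 65% v 35%.** Fisher's test stayed at 90.7-90.9% throughout.

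| Assumed spread across strata, both arms | Stratified CMH |
|---|---|
| none | 91.3% |
| ±6.5 points | 91.7% |
| ±15 points | 93.2% |
| ±25 points | 96.0% |

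CMH type I error was 4.9-5.0%. Fisher's was 3.4-3.9% in runs with a 30/40/30% grade mix, so part of the gain comes simply from leaving a conservative test. In one run at ±15, Fisher gave 90.7%, unstratified chi-square 91.6% and stratified 93.1%: 0.9 of the 2.4 points were not due to baseline. These figures are for the CMH test on complete data.

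**5. How large might the spread be?** Under a latent rating-error model near the stated agreement, an untreated temple is re-rated at least one grade better 9-15% of the time from Grade 2 and 26-39% from Grade 4. The half-spread for one temple is (26 - 9)/2 = 8.5 to (39 - 15)/2 = 12 points. Response needs both temples. If their rating errors are independent, the rates are squared: 0.8-2.3% and 6.8-15.2%, a half-spread of about ±3 to ±6.5. Correlated errors fall in between. Rating error alone therefore does not reach ±15.

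**6. Chance imbalance.** For a one-third stratum at 112/56, the SD of the between-arm difference is √[(1/3)(2/3)(1/112 + 1/56)] = 0.077, so a gap of 10 points or more has about 19% probability (25% at 90/45). If the 10 points move between the extreme strata, the estimate shifts by 0.10 × 30 = 3 points at ±15, or 0.10 × 50 = 5 points at ±25.

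**7. FACE-Q.** For one visit with equal variances and baseline-to-follow-up correlation r, the variance of change is proportional to 2(1 - r), and to 1 - r² with baseline adjustment. The ratio is (1 + r)/2: 0.65, 0.75 and 0.85 at assumed r of 0.3, 0.5 and 0.7.

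**The case against.** The strongest reply is that nothing is broken. Randomization makes the unadjusted Fisher test valid, it meets its power target, and protocol 9.2 calls 65% conservative and 35% an upper limit. That stands: a reader might infer that the primary analysis is biased or underpowered, and the documents support neither.

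The gain may also be small. Exclusion 1.01 removes people judged unable to gain a grade, volume is tailored to the degree of hollowing (protocol 4.3), and touch-up is allowed, all of which may flatten any gradient in the treated arm. With a ±12-point spread in the control arm only, unstratified chi-square had 91.7% power and stratified CMH 91.5%; with ±12 in opposite directions by arm, 91.8% and 91.3%. Against chi-square, then, stratifying can lose slightly. Against the planned Fisher test it had no less power in any case tried.

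Three further inferences go too far:
- The imputation model's use of baseline ATHS does not show that response depends on it. That model predicts the Month 6 score, not the change.
- The FACE-Q model cannot be said to leave out baseline. Its terms are simply not listed.
- No figure links baseline ATHS to GAIS, which is already judged against baseline photographs (protocol 8.1.3).

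**Conclusion.** The point holds as one of efficiency. The primary comparison does not use a covariate that every mITT participant has and that randomization does not balance. The benefit runs from about half a power point over Fisher if baseline is not prognostic, to about 2 points at ±15 and 5 at ±25, with a variance rise of 1-3% in the worst cases tried. The larger figures need a gradient beyond what rating error alone supports, and all of them rest on an assumed grade mix and an assumed spread that is the same in both arms.

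For GAIS, a benefit is possible but not shown. For FACE-Q, the defect is an incomplete model specification; the 15-35% variance reduction applies only if baseline would otherwise be omitted, and the p-values are nominal.

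**What to change.** Before database lock:
- **SAP 8.3.2 Step 3 and 8.3.3.** Stratify each imputed dataset's PROC FREQ table by baseline ATHS. Fix in advance how the two temples' grades form a stratum (for example the worse temple, as SAP 8.5 already does for descriptive summaries) and when a stratum with too few participants in either arm is merged.
- **Pooling.** Pass the Mantel-Haenszel common risk difference and its standard error to MIANALYZE for the estimate, CI and p-value. The CMH chi-square cannot be pooled directly. If nothing is missing, run the same analysis on the single dataset. The resulting Wald p-value can run slightly above nominal size, so check its type I error by simulation.
- **Fisher's test.** Keep it as supportive. Update protocol 9.4.2.2 or record the change in SAP Appendix C. The sample size can stay as it is.
- **GAIS.** The same stratification is optional.
- **SAP 8.4.** State the FACE-Q model terms: treatment, visit, treatment-by-visit, baseline score and baseline-by-visit.

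The cost is document wording, one derived variable and a small variance penalty if baseline proves uninformative. No new data are needed.

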### 9.4.2.3. Sensitivity Analyses

Since multiple imputation will be used for the primary analysis if the observed dataset is not complete for the primary endpoint, a sensitivity analysis will then be done using observed data, without imputation of missing data.

If so, a second sensitivity analysis will be done after imputation for missing data by baselineobservation carried-forward (for reversion to baseline), which effectively handles participants with missing primary effectiveness as nonresponders.

The primary analysis using 2-sided Fisher's exact test or multiple imputation (depending on whether any participants have missing primary effectiveness endpoint as mentioned in Section 9.4.2.2) will also be repeated on the PP population as a third sensitivity analysis.

#### 9.4.3. Secondary Endpoints

Secondary effectiveness endpoints:

- Responder status based on the EI's assessment of the temple area using GAIS at Month 6 after last treatment for treatment group and after randomization for control group, where a "responder" is a participant with grade "improved" or "much improved" on GAIS.
- Responder status based on the participant's assessment of the temple area using GAIS at Month 6 after last treatment for treatment group and after randomization for control group, where a "responder" is a participant with grade "improved" or "much improved" on GAIS.
- Change from baseline on FACE-Q Satisfaction with Facial Appearance questionnaire at Month 6 after last treatment for treatment group and after randomization for control group.
- Change from baseline on FACE-Q Satisfaction with Temples questionnaire at Month 6 after last treatment for treatment group and after randomization for control group.

The following analysis will be performed for the secondary effectiveness endpoints:

- For the responder status based on the EI's and participant's assessments of GAIS at Month 6, the responder rates with 95% exact CI will be summarized, and p-value for between treatment group comparisons will be based on 2-sided Fisher's exact test using observed data.
- Change from baseline on participant responses on FACE-Q Satisfaction with Facial Appearance and with Temples questionnaires, for the Rasch-transformed score (0-100), will be analyzed using a repeated measures mixed-effects model, and the p-value for the between treatment group comparison will be provided for Month 6.

CONFIDENTIAL JUVÉDERM® VOLUMA® with Lidocaine injectable gel

#### 9.4.4. Additional Endpoints

Other effectiveness endpoints:

- Primary and secondary measures at other visits
- Full-scale ATHS scores at each measurement visit
- Full-scale EI assessment of GAIS at each measurement visit
- Full-scale participant assessment of GAIS at each measurement visit
- Percentage of participants showing improvement on the FACE-Q Satisfaction with Facial Appearance questionnaire, for the Rasch-transformed score, at each measurement visit
- Participant responses to FACE-Q Satisfaction with Facial Appearance questionnaire, for the Rasch-transformed score (0-100), unadjusted for baseline, at each measurement visit
- Percentage of participants who respond as Somewhat Satisfied or Very Satisfied for 3-5 items (to be specified in the SAP) on the FACE-Q Satisfaction with Facial Appearance questionnaire at Month 6
- Percentage of participants showing improvement on the FACE-Q Satisfaction with Temples questionnaire, for the Rasch-transformed score, at each measurement visit
- Participant responses to FACE-Q Satisfaction with Temples questionnaire, for the Rasch-transformed score (0-100), unadjusted for baseline, at each measurement visit
- Percentage of participants who respond as Somewhat Satisfied or Very Satisfied for 3-5 items (to be specified in the SAP) on the FACE-Q Satisfaction with Temples questionnaire at Month 6
- Participant's satisfaction with treatment questions and age perception question, at each measurement visit
- Volume change of each temple from baseline as assessed by 3D imaging, at each measurement visit

The following analyses will be performed for the other effectiveness variables. There are 5 variables underlying the primary and secondary variables:

- Overall score of ATHS at each measurement visit, baseline and change from baseline, summarized with response frequencies and descriptive statistics for each treatment group, using the temple with worse baseline score to represent the participant (using the left side if both temples have the same baseline score).
- Overall score of EI assessment of GAIS at each measurement visit, baseline and change from baseline, summarized with response frequencies and descriptive statistics for each treatment group.
- Overall score of participant assessments of GAIS at each measurement visit, baseline and change from baseline, summarized with response frequencies and descriptive statistics for each treatment group.

- Participant responses to FACE-Q Satisfaction with Facial Appearance questionnaire, for item-level scores for ordinal categories from 1 to 4 for each of 10 items at each measurement visit, baseline and change from baseline, summarized with response frequencies and descriptive statistics for each treatment group.
- Participant responses to FACE-Q Satisfaction with Temples questionnaire, for item-level scores for ordinal categories from 1 to 4 for each of 12 items at each measurement visit, baseline and change from baseline, summarized with response frequencies and descriptive statistics for each treatment group.

Other analyses for additional endpoints will be detailed in the SAP.

